1.0 Objectives

The Institute of Medicine report "Dying in America" called for the development of interventions to increase effective advance care planning (ACP) and shared decision making among adolescent and young adult (AYA) patients.(1-3) Such interventions aim to help AYAs and their caregivers discuss goals of care together to make sure patients receive medical care "consistent with their values, goals, and informed preferences."(1, 2) Communication surrounding preferences and goals of care and subsequent decision making is formalized in ACP, a process involving the provision of verbal or written information informing individuals about possible medical options such as cardiopulmonary resuscitation (CPR) or mechanical ventilation.(4-6) However, this ACP process is often inadequate as it is presently conducted, particularly for AYAs.(7-10)

Our research group has developed and studied video decision aids to assist patients with advanced cancer and their caregivers in making important decisions about their medical care.(11-25) Video can improve decision-making by providing visual information to present complex medical and emotional scenarios; a growing body of evidence supports the feasibility and effectiveness of using video aids in medical decision making.(2) Video enhances patients' and caregivers' understanding of complex health information by providing realistic visual images that can facilitate their education about hospitalizations, intensive care unit (ICU) admissions, and medical procedures, leading to greater concordance of preferences between patients and caregivers and improved caregiver outcomes in bereavement. Our work has shown that among adult patients, these videos can educate patients and family caregivers about their care options more effectively than verbal-only explanations, enhance their knowledge about medical interventions, and improve patient-caregiver concordance.(11-25)

We have developed a video decision aid for AYAs and their caregivers that reviews treatment options and begins to discuss goals and preferences for their care. The overall objective of this study is to conduct a randomized controlled trial of the video (vs. usual care) in 50 dyads of AYA with advanced cancer and their caregivers. Our hypothesis is that the video better informs patients and caregivers of their options, leads to more ACP conversations, engagement and documentation, and leads to more congruent decision making between AYA and caregivers (primary outcome). Demonstrating the effectiveness of using a video aid in this pilot provides evidence for conducting a larger trial integrating such a video into clinical practice. The

Specific Aims are:

Aim 1: To compare knowledge, preferences and decisional conflict among 50 dyads of AYA with advanced cancer and their caregivers randomly assigned to one of two ACP modalities: 1. The newly created video depicting various goals of care (intervention, 25 dyads), or 2. usual care (control, 25 dyads).

Hypothesis H1a: Patients and caregivers randomized to the video will have higher congruence of preferences between patient and caregiver dyads compared to dyads in the control group (primary outcome). H1b: Those randomized to the video group will have

higher knowledge, fewer preferences for life-prolonging interventions and lower decisional conflict than those randomized to the control group.

Aim 2: To compare ACP conversations between patients with their health care team and caregivers, and ACP documentation between intervention and control dyads. H2: Patients randomized to the video will have more ACP conversations and higher levels of engagement, and more ACP documentation after 3 months.

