ACP engagement: We will ask four validated questions to patients only regarding ACP engagement (How ready are you to talk to your caregiver? To your doctor? To appoint a surrogate? To sign an ACP document?).(54) (Appendix D, page 4; Appendix H, page 2).

Comfort with the video: For those patients and caregivers randomized to the video, we will measure acceptability of the decision aid using four questions regarding comfort viewing the video, which we have validated in our prior work.(11, 13, 15, 17, 20-22, 25, 46) (Appendix H, page 4).

Additional outcomes: AYA-reported ACP conversations with caregivers and clinicians will be assessed after three months from baseline survey. Both patients and caregivers will be asked about ACP conversations (Appendix I, bottom of page 3).

Data collection protocol: Based on our prior work, data collection is estimated to take no longer than 40 minutes (10 minutes for informed consent and screening; 10 minutes for baseline assessment; 10 minutes for ACP modality; 10 minutes for immediate follow-up interview) and will be conducted in the outpatient setting. The relatively brief interviewing time (40 minutes) in which the survey is conducted should assure completion of the interview without burdening participants. We do not foresee the additional time to complete the survey to be a barrier to successful recruitment and completion of the protocol.

Participants will be provided written copies of the questions or the questions will be shared with them over zoom (using the "share screen" feature) in order to follow along

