Aim 1: H1: AYA with advanced cancer and caregivers randomized to the video will have higher concordance between patients and caregivers (Primary Outcome), and more likely to have higher knowledge, make decisions for less burdensome care (i.e., limited or comfort care, no CPR, no ventilatory support), have lower decisional conflict, and engagement, than those randomized to the control group. Preference concordance between patient and caregiver will be treated as a dichotomized variable and compared between the two study arms using a chi-square test. We will conduct separate analyses for patients and caregivers for secondary outcomes. Knowledge score, decision conflict scale, and ACP engagement will be considered as continuous variables. We will use twosample t-tests or Wilcoxon rank sum tests, whichever more appropriate, to compare the distribution between the two study arms. Chi-square tests will be used to compare the proportion of patients/caregivers choosing less burdensome care between the two study arms. We will explore the effect of patient characteristics (age, sex, etc.) in choosing less invasive care using a logistic regression model. In this study, we will treat sex as selfreported gender and will conduct a sex-based analysis of intervention effects to explore sex as a biological variable. *Power analysis*: Assuming 50% of control arm achieve preference concordance between patients and caregivers, the study will have 80% power to detect a 41% difference (50% vs. 89%) in concordance. Assuming 68% of control patients/caregivers choose non-life prolonging care, the study will have 82% power to detect a 31% difference (68% vs. 99%) in preferences between the two arms. For the continuous outcomes (knowledge, decisional conflict, ACP engagement), the study will have 80% power to detect an effect size of 0.81 with 25 subjects per group.

Aim 2: *H2.* Patients randomized to the video will have more ACP conversations and documentation after 3 months. We will treat conversations and documentation as continuous variables. Assuming 50% of controls achieve ACP conversations/documentation between baseline and three-month follow-up, the study will have 81% power to detect a 27% difference (50% vs. 77%) between the two study arms.

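### The Aim 2 comparison of 3-month ACP conversations and documentation uses no baseline value, although matching ones appear to be collected; adjustment would bring a modest gain in precision at almost no cost

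*Combined protocol and SAP*

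**What the plan says.** Section 1.0, Aim 2, states the hypothesis: "Patients randomized to the video will have more ACP conversations and higher levels of engagement, and more ACP documentation after 3 months". The analysis is in the Aim 2 paragraph of Data Analyses (section 8.0). It says "We will treat conversations and documentation as continuous variables" and then gives a power figure for two proportions: "the study will have 81% power to detect a 27% difference (50% vs. 77%) between the two study arms". It names no test, model or covariate. The only regression on patient characteristics in that section is exploratory and concerns the Aim 1 choice of less invasive care.

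Two sources of matching baseline data are described:

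- **Readiness.** Section 8.0 says "We will ask four validated questions to patients only regarding ACP engagement", and lists them: "How ready are you to talk to your caregiver? To your doctor? To appoint a surrogate? To sign an ACP document". The reference is "Appendix D, page 4; Appendix H, page 2". Section 7.0 identifies Appendix D as the questionnaire completed before the intervention and before randomisation.
- **Documentation.** Section 7.0, at the end of the control-arm text, has the patient's medical record read at baseline and again after 3 months to determine ACP documentation.

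Two other places do not list readiness at baseline. Table 1 shows ACP engagement only in the block after exposure. The Overview of the Trial (section 2.0) names knowledge, preferences and decisional conflict as the before-and-after measures and leaves engagement out.

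**The concern.** Three of the four readiness items correspond to Aim 2 outcomes: conversations with the caregiver, conversations with clinicians, and documentation. A patient who says at enrolment that they are ready to talk or sign may well be likelier to have done so by 3 months, whichever arm they are in. Randomisation is stratified by race and ethnicity only, so readiness is not balanced by design, and in a small trial the arms can differ on it by chance. An unadjusted comparison carries that difference into the estimate, and its standard error is wider than it need be. The pilot is meant to inform a larger trial, so an estimate shifted by several points on a 27-point target matters, even though no single confirmatory decision hangs on it.

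**Working it through.** **Inputs.** 25 patients per arm (section 1.0, Aim 1: "The newly created video depicting various goals of care (intervention, 25 dyads), or 2. usual care (control, 25 dyads"); 50% vs 77% and 81% power (Aim 2 power statement). Not given, so assumed: two-sided 5% level; no loss to follow-up; and the correlation r between baseline readiness and the normal variable underlying the yes/no outcome, shown from 0.3 to 0.6.

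**Step 1: the plan's own figure.** Mean proportion = (0.50 + 0.77)/2 = 0.635.

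- At 25 per arm, the null SE is √(2 × 0.635 × 0.365/25) = 0.136 and the alternative SE is √((0.25 + 0.1771)/25) = 0.131. Power = Φ((0.27 − 1.96 × 0.1362)/0.1307) = Φ(0.02) = 0.51. The exact power of the uncorrected chi-square test is 0.54.
- At 50 per arm, the same formula gives 0.81.

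The stated 81% therefore corresponds to 50 per arm, twice the number of patients in each arm.

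**Step 2: chance imbalance.** The arm difference in mean readiness, in SD units, has SD √(2/25) = 0.283. An imbalance of at least 0.4 SD in either direction has probability P(|Z| > 0.4/0.283) = 0.157. With no true effect and a 50% rate, an imbalance of 0.4 SD moves the unadjusted difference by r × 0.399 × 0.4, where 0.399 is the normal density at zero. That is 4.8 points at r = 0.3, 8.0 at r = 0.5 and 9.6 at r = 0.6. In simulation at r = 0.5, adjustment leaves about 0.7 of the 8.0 points.

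**Step 3: what adjustment gains.** Simulation with 20,000 trials per setting: a five-level readiness item, a binary outcome, and a linear model on arm plus readiness. Percentage cuts come from unrounded standard errors (SE).

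| r | SE with no effect, unadjusted → adjusted | SE at 50% vs 77% | Cut in SE | Power, adjusted |
|---|---|---|---|---|
| 0.3 | 0.142 → 0.139 | 0.131 → 0.130 | 1–2% | 52–54% |
| 0.5 | 0.142 → 0.133 | 0.130 → 0.123 | 5–6% | 57% |
| 0.6 | 0.141 → 0.126 | 0.130 → 0.119 | 9–11% | 60–61% |

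The power ranges cover repeat runs. The unadjusted t-test has about 54% power throughout, but its size is about 6.5%; the adjusted test keeps close to 5%. At r = 0.7 the adjusted power is about 65%.

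**Step 4: sensitivity to the meaning of r.** If r is instead the correlation with the observed yes/no outcome, the variance is multiplied by (1 − r²)(1 + 1/46). At r = 0.5 that is 0.75 × 1.022 = 0.77, with power about 0.63; at r = 0.7 power is about 0.79. This is a stronger association than the same r in the table: a latent r of 0.5 corresponds to about 0.5 × 0.399/0.5 = 0.40 with the observed outcome at a 50% rate, before readiness is grouped into five levels.

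These figures concern readiness. None is offered for baseline chart documentation, because the documents do not say how common it is.

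**The case against.** The strongest reply is that the unadjusted comparison is valid. Randomisation makes it unbiased on average, and its standard error already allows for chance imbalance. In a 50-dyad pilot, where the Overview says conversations and documentation will be explored (Table 1 labels conversations secondary), adjustment is a refinement. The documents give no correlation, and at 0.3 or below there is nothing to gain in power. All of this stands, and it limits the point to a modest one. It does not remove it, because the change is nearly free and the Aim 2 paragraph names no method that it would displace.

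A second reply is that baseline readiness may not be collected. Section 8.0's reference to Appendix D supports it; Table 1 and the Overview do not. Table 1's baseline block also omits decisional conflict, which the Overview says is measured before and after, so the table is not a complete list. That weakens the table as counter-evidence but does not settle the matter, and the Overview omits engagement too. Appendix D is not among the pages available.

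A third reply is that larger matters come first: the outcomes are called continuous but powered as proportions, and the 81% does not follow from 25 per arm. This is right, and the first must be settled before a risk difference can be reported.

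A reader might infer that the planned comparison is biased, or that adjustment would rescue the power of Aim 2. Neither follows. The imbalance is a conditional error that can go either way, and the table stays far below 81%.

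**Conclusion.** The point holds as a recommended improvement of modest size. The plan leaves unused a baseline chart value that it says it collects and readiness items that it appears to collect. The cost is some precision, and an estimate exposed to chance imbalance: about 8 points for a 0.4 SD imbalance at r = 0.5, with an imbalance at least that large in about 16% of trials. Adjustment does not close the gap between 81% and the 51–54% that 25 per arm provides.

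This rests on binary outcomes, 25 patients per arm with complete follow-up, a two-sided 5% level, and an assumed r. The Missing Data section expects some loss at 3 months, which would lower all the power figures. If r is 0.3 or less, the practical gain is negligible.

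**What to change.** In the Aim 2 paragraph of Data Analyses:

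1. Define conversations with the caregiver, conversations with clinicians, and documentation as binary outcomes, in line with the 50% vs 77% power statement, and drop the continuous label. State whether documentation means any on record at 3 months or only what is new since baseline.
2. Estimate each arm difference among patients as an adjusted risk difference with 95% CI, from a regression on arm plus one pre-specified baseline covariate. Use readiness to talk to the caregiver for caregiver conversations, readiness to talk to the doctor for clinician conversations, and baseline chart documentation for 3-month documentation. Use readiness to sign for documentation only if baseline documentation is nearly constant.
3. Report the unadjusted proportions by arm alongside.

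Reconcile Table 1 and the Overview of the Trial with the ACP engagement text, so that the readiness items are listed at baseline. Fix the covariates before outcome data are compared by arm.

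The cost is wording and one degree of freedom per model. No new data are needed if Appendix D carries the items as cited; if it does not, four short questions to patients would have to be added before randomisation. The downside is a negligible gain if the covariate is only weakly related to the outcome.

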2.0 Background

AYA oncology patients often receive intensive medical services at the end of life (EOL).(26-28) Compared to younger children, AYA oncology patients have higher rates of hospitalization, more frequent ICU admissions, and receive more chemotherapy treatments during the last 30 days of life. (27, 28) To date, the majority of AYA cancer deaths occur in the hospital and minority race, Hispanic ethnicity, and hematological malignancy increased the odds of dying in the inpatient setting. (29) Palliative care has been associated with receipt of less intensive interventions at the EOL in hospitalized AYA patients with cancer, possibly due to the facilitation of greater AYA involvement in communication and decision-making.(26) A growing body of research suggests that AYA patients identified a spectrum of possible roles in medical decision-making, with the majority preferring an active role while still expressing a desire for parental presence in decision-making.(30) Fulfilling the roles of "good child" and "good patient" may impact AYA decision-making, adherence to medical treatment plans, and social interactions.(31) As a part of fulfilling these roles and in the absence of communication between patients and their caregivers around preferences and goals of care, AYAs may continue intensive therapies.(32, 33) ACP tools have been developed to facilitate ACP discussions between patients and their caregivers around preferences for care at the EOL,(32, 33) but these tools remain underutilized in the clinical setting. In the only randomized controlled trial of an ACP tool in AYA patients with cancer, patients randomized to receive the intervention (consisting of three, 1-hour family-centered ACP sessions and the Five Wishes tool), had statistically greater congruence to limit treatments in various clinical scenarios.

The lack of ACP is associated with greater use of intensive or burdensome interventions, more hospitalizations at the EOL, lower palliative care use, and worse family bereavement outcomes.(34-38) Unfortunately, ACP communication between AYA and their caregivers remains inadequate.(2) For the ACP process to lead to optimal decisions, AYA and caregivers require engaging, accurate, impartial and comprehensible information about treatment options, and a care setting where communication needs are addressed early in their illness.(39-42) However, studies show that traditional written and verbal ACP do not effectively engage or inform patients and their caregivers.(2) Patient understanding may also be clouded due to developmental needs and stage, psychological distress, and the inability to realistically envision accurate future health states.

The traditional approach to ACP, which primarily relies on *ad hoc* verbal descriptions of hypothetical clinical situations and treatment choices, is limited because complex scenarios are difficult for AYAs and caregivers to envision, clinician information is inconsistent, and verbal explanations are hampered by literacy, emotional and language barriers.(41, 43, 44) Over the past few years, investigators have recognized the shortcomings of prior efforts and have developed new interventions to better facilitate ACP in adult patients.(11-15, 17-23, 25, 45-47) The video intervention proposed for this study focuses on treatments for AYAs with advanced cancer. Video decisions aids to better educate and inform decision-making are commonly used. To the best of our knowledge, this is the first use of an ACP video decision aid in AYAs.

For AYAs and their caregivers to have informed ACP conversations about patient preferences, both patients and caregivers need accurate information presented in a standardized and easy to understand manner. Presently, clinicians do not provide any routine or standardized information about goals of care to AYAs or caregivers. AYAs and their caregivers often receive intensive interventions as a default option, without a shared decision-making conversation or awareness of different treatment options or blended goals of care. Poor ACP and communication about AYA preferences for end-oflife care contribute substantially to the receipt of intensive medical care and possibly increased suffering at the EOL. Therefore, improving ACP with a standardized video decision aid that accurately informs AYAs and their caregivers about ACP decisions may prove to be an effective strategy to enhance the delivery and quality of medical care for AYAs with advanced cancer and their caregivers. ACP video tools have shown promising efficacy in educating patients and caregivers about their options and informing their preferences for care. This study has the potential to improve the concordance of AYAs and caregiver preferences leading to better shared decision making and ultimately the delivery of AYA-centered care that is consistent with the patient's values.

Preliminary Studies in cancer: Over the last decade, the research team has focused on improving decision making for persons with serious illness by creating and studying innovative decision aids. The work cited below demonstrates the research team's experience, commitment, and ability to use effectively a wide array of clinical research methods to design, administer, and complete projects focused on serious illness.

The first video our team produced was a 5-minute decision aid depicting the goals of care for adults with cancer.(20) In a randomized controlled trial, patients with advanced cancer were randomized to either listen to a verbal description of the goals of care (N=27) or view the video decision aid (N=27), and then asked the level of care they would want. The three levels of care included: life-prolonging care (hospitalization, intensive care unit); limited care (hospitalization but no ICU); or, comfort care (symptom relief only). We also assessed uncertainty regarding decision making using the Decisional Conflict Scale with scores ranging from 3 (high uncertainty) to 15 (no uncertainty). End points were the selected goal of care in each arm of the study, uncertainty in decision making, and comfort viewing the video. Patients in the video arm (vs. control) were more likely to opt for comfort care, were more informed, and more certain of their decision. Among patients receiving the verbal narrative, 26% desired life-prolonging care, 52%

chose limited care, and 22% preferred comfort care. In the video group, none desired lifeprolonging care, 4% chose limited care, 92% preferred comfort care, and, 4% were uncertain (P < 0.001). Participants in the video group had less uncertainty (mean uncertainty score, 13.7; [95% CI, 12.8 to 14.6]; P = 0.002) compared to participants randomized to the verbal group (mean uncertainty score, 11.5; [95% CI, 10.5 to 12.6]). Of the patients randomized to the video group, 82% felt "very comfortable" watching the video, and 82% would "definitely recommend" the video to other patients. Based on this work, the research team completed a larger NCI trial that was published in the *Journal of Clinical Oncology* and presented as an oral abstract at ASCO.(15) [name] is leading a larger trial of this video decision aid in 4,500 patients with advanced cancer along with the adult palliative care team at Dana Farber Cancer Institute.

Overview of the Trial: This study is a randomized trial of the video in 50 AYAs with advanced cancer and their caregivers that will assess preferences for care in advanced cancer and concordance rate of preferences between dyad. We will randomly assign dyads to one of two ACP modalities: 1. the ACP video decision aid (intervention), or 2. Usual care. Patients' and caregivers' knowledge, preferences (goals of care, CPR, ventilation), and decisional conflict be assessed before and after exposure to the video or control ACP modality. Telephone-based interviews will be conducted at 3 months to assess patients' and caregivers' preferences, ACP conversations with caregivers and clinicians, and the medical record will be queried to examine ACP documentation. The primary outcome is AYA and caregiver concordance regarding treatment preferences for advanced cancer (Aim 1). Secondary outcomes include knowledge, preferences, decisional conflict, and ACP engagement (Aims 1 and 2). We will also explore the stability of preferences, presence of ACP conversations and documentation after 3 months (Aim 2). We hypothesize that the video decision aid better informs patients and their caregivers and leads to more informed decision making.

